7.7.2 Reasons for Withdrawal or Termination

A subject may discontinue his or her participation without giving a reason at any time during the study. Should a subject's participation be discontinued, the primary reason for termination must be recorded in the eCRF. In addition, efforts should be made to perform all procedures scheduled for the Month 6 visit if discontinuation is prior to that visit, or the year 5 visit if discontinuation is after year 4 but before year 5. Subjects who are withdrawn may be replaced with new subjects for evaluation upon Sponsor approval.

The primary reason for discontinuation or withdrawal of the subject from the study should be noted using the following categories:

- Lost to follow-up. The subject did not return to the clinic and attempts to contact the subject were unsuccessful. Attempts to contact the subject must be documented
- Voluntary withdrawal. The subject wishes to withdraw from the study. The reason for withdrawal, if provided, should be recorded in the eCRF. NOTE: All attempts should be made to determine the underlying reason for the withdrawal and, where possible, the primary underlying reason should be recorded
- Principal Investigator withdrawal due to failure to comply with trial requirements or subject is uncooperative or refuses to continue in the trial
- Study termination. The sponsor, IRB/ IEC, or regulatory agency terminates the study
- Other (NOTE: The specific reasons should be recorded in the eCRF)

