5.2. Key Definitions

Age

Age at screening is derived in the database and this value will be used for all analyses.

Definition of Baseline for safety assessments

Baseline will be defined as the last available value prior to the implant of Cordella PA Sensor and may be at any visit between Screening (V1) and Cordella PA Sensor Implant Visit (V2).

Definition of Baseline for PAP measurements

Baseline will be defined as value at Implant Visit (V2) obtained before discharge .

Change from Baseline

Absolute change from baseline:

Absolute change = Post-baseline value –baseline value

Time to Onset of AE

Time to onset of AE [days] = Date of start of AE – Date of implant of Cordella PA Sensor + 1

Start Day of concomitant medication

If medication starts before date of implant of Cordella PA Sensor:

Start Day of Medication = Date of start of medication – Date of implant of Cordella PA Sensor

If medication starts at/after date of implant of Cordella PA Sensor

Start Day of Medication = Date of start of medication – Date of implant of Cordella PA Sensor + 1

Incomplete start dates of medication will not be imputed. Start day of medication will be missing.

Stop Day of concomitant medication

If medication stopped before date of implant of Cordella PA Sensor:

Stop Day of Medication = Date of end of medication – Date of implant of Cordella PA Sensor

If medication stops at/after date of implant of Cordella PA Sensor

This document is confidential.

Stop Day of Medication = Date of end of medication – Date of implant of Cordella PA Sensor + 1
Incomplete end dates of medication will not be imputed. Stop day of medication will be missing.

Definition of study completed/discontinued/ongoing

A subject will be defined as study ‘completed’/‘discontinued’ based on the eCRF information. At the time of the pre-defined main analysis, subjects which are ongoing at date of cut-off will be counted as ‘ongoing’.

Time since first diagnosis of heart failure

Time since diagnosis [months] = ((Date of Screening – Date of first HF diagnosis)+1)/30

Exposure time:

which would be exact 6 or 12 months (180 or 365 days respective) post-implant visit for subjects who are still in the study at/after this timepoint.

which would be [date of last available date – date of Implant visit + 1] for subjects who withdraw from study prior to month 6 or 12 (180 or 365 days respective) post-implant visit.

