7.1.1. Main analysis

The mathematical statement of the null and alternative hypothesis is as follows:

$$H_0: r_6 \geq PG_6$$

$$H_A: r_6 < PG_6$$

will be used for the goal. The null hypothesis will be rejected if the upper confidence bound for the rate is less than the performance goal, or equivalently, that the corresponding p-value from the hypothesis test is less than 0.025. An observed rate of less than 0.37 and rejection of the null hypothesis indicate that the observed rate is statistically less than the performance goal, indicating clinically acceptable results and study success. Analysis will be based on a Poisson regression approach for the number of events, with the exposure time as an offset term, where r_6 is the 6-month rate of primary endpoint events and PG_6 is the performance goal. A value of 0.43 will be used for the goal.

The test will be based on each subject's total number of events, treatment arm, and exposure time, where a subject's exposure is the time to death, early study discontinuation or 6 months, whichever is smaller.

```
proc genmod data = xxx;  
    model number of events = dummy /*(dummy variable)*/ / noint type3 dist=poisson  
offset=log(exposure_time);  
run;
```

All events until day x, which would be exact 6 months (180 days) post-implant visit would be summarized by cohort. The estimated 6 month incidence of HF related hospitalizations (HFH) or all-cause mortality, along with the 2-sided 95% CIs for the estimated will be presented, and p-value from the hypothesis test. The presentation will also include number of HFH, all-cause mortality, total number of both events, and subjects' event rate of HFH or all-cause mortality is calculated as the total number of observed events per subject divided by the (subject's observed exposure time/180) from implant through 6 months, where a subject's exposure is the time to death, early study discontinuation or 6 months (180 days) post implant visit, whichever is the smallest.

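### SAP 5.2 and SAP 7.1.1 end the exposure of early leavers at different dates; if discontinuation is recorded after the last contact, the 7.1.1 wording lowers the primary rate

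*SAP*

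**What the plan says.** SAP 5.2 (Key Definitions, exposure time) has two rules. Full exposure of 180 or 365 days goes to the "post-implant visit for subjects who are still in the study at/after this timepoint". For those who withdraw before then, exposure is "date of last available date – date of Implant visit + 1". The last available date is not defined, and death is not mentioned.

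SAP 7.1.1 specifies a "Poisson regression approach for the number of events, with the exposure time as an offset term" and says that a subject's "exposure is the time to death, early study discontinuation or 6 months, whichever is smaller". It repeats the rule for the displayed subject rate, where events are "divided by the (subject's observed exposure time/180) from implant through 6 months". SAP 7.1.6 (cohort comparison) and 7.1.11 (days alive and out of hospital) also stop at early study discontinuation. SAP 7.1.4, 7.1.8, 7.1.9 and 7.1.12 contain no rule of their own for the count analysis and follow the primary.

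Protocol 7.7.2 describes lost to follow-up thus: "The subject did not return to the clinic and attempts to contact the subject were unsuccessful". SAP 5.3 says that dropouts are censored but gives no date.

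**The concern.** Lost to follow-up can be declared only after contact attempts have failed, so the recorded discontinuation can be later than the last date on which anything was known about the subject. Read literally, 7.1.1 counts the days in between as exposure. HF hospitalisations and deaths in those days are unlikely to reach the database, so the denominator grows without a matching chance of events.

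The primary rate is compared with fixed limits: the upper confidence bound must be below 0.43 and the observed rate below 0.37. There is no control arm in which the same error would cancel, so extra exposure always favours success.

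No planned efficacy analysis would reveal the effect. The negative binomial sensitivity analysis (SAP 7.1.2) keeps the same terms, and hence the same offset. The extreme-case and tipping-point analyses in SAP 5.3 and 8.1.2 concern only the safety endpoints, although Protocol 10.8 promises sensitivity analyses for missing data in general.

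The count analyses are also out of line with the rest of the SAP. The Kaplan-Meier analyses in 7.1.9 censor at the last available date, 7.1.10 censors all-cause mortality at the last date known alive, and 8.1.1 censors at the last available date or day 180.

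**Working it through.** **Inputs from the documents.** 450 implanted and 406 evaluable, so 44 (9.8%) not evaluable; dropout about 10% by 6 months (Protocol 6.1); goal 0.43; one-sided alpha 0.025; observed rate below 0.37; assumed rate 0.34.

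**The plan's own figure.** An exact one-sample Poisson test with 406 six-month units rejects at 148 events or fewer. Its actual alpha is 2.2% and its power at 0.34 is 81.4%, which agrees with the stated power above 80%.

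**Assumptions not in the documents.** The lag L from last contact to recorded discontinuation, the share s of dropouts who have such a lag, and no event learned of during the lag. Dropouts are treated as alive when they leave.

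**Effect on the rate.** Take 45 dropouts (10% of 450) whose last contact is spread evenly over 180 days. True exposure in six-month units is 405 + 45 × 0.5 = 427.5. A lag truncated at day 180 adds on average L − L²/360 days, so

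added units = 45 × s × (L − L²/360) / 180, and relative rate = 427.5 / (427.5 + added).

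The one-sided error is the probability of meeting both success conditions at a true rate of 0.43, with a log-scale Wald upper bound. It comes from simulation, with 20,000 to 200,000 trials per setting; separate runs differ by 0.1 to 0.3 points.

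| Share with lag | Lag (days) | Added units | Change in rate | One-sided error |
|---|---|---|---|---|
| none | 0 | 0 | 0 | 2.1–2.3% |
| quarter | 14 | 0.84 | −0.2% | about 2.5% |
| quarter | 30 | 1.72 | −0.4% | 2.6–2.7% |
| quarter | 60 | 3.13 | −0.7% | 2.8% |
| half | 60 | 6.25 | −1.4% | 3.5% |
| all | 30 | 6.88 | −1.6% | 3.7–4.0% |
| all | 60 | 12.5 | −2.8% | 5.3–5.5% |

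**Second model, as a check.** Let all 44 non-evaluable subjects have last contact at day 90 on average. Exposure is 406 + 44 × 90/180 = 428.0 units. A 30-day lag gives 406 + 44 × 120/180 = 435.3 (rate −1.7%), and a 60-day lag gives 442.7 (−3.3%). The error is 2.3% with no lag, 3.9% at 30 days and 6.3% at 60.

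**Can it change the result?** Under the same model, the largest event count that meets both conditions is 157 with no lag, 160 with 30 days and 163 with 60. For example, 159 events give:

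- exposure to last contact: 159/428.0 = 0.3715, upper bound 0.3715 × exp(1.96/√159) = 0.434, fail;
- 30 days added: 159/435.3 = 0.3652, upper bound 0.427, pass.

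The choice of date therefore matters only for a narrow band of counts near the limits.

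**The case against.** The best counter-argument is that there may be no conflict. SAP 5.2 is the general definition of exposure time. SAP 7.1.1 could be naming the stopping events while 5.2 supplies the date, and 7.1.1 itself speaks of observed exposure time. Because the last available date is undefined, the two rules could be programmed identically. That reading is fair. It does not remove the point, because another programmer could follow 7.1.1 literally and obtain a different primary rate.

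A reader might infer that discontinuation is recorded weeks to months after the last information, and hence that the one-sided error exceeds 2.5%. The documents do not support this. They state no interval and do not say which date the study-completion form records for a lost subject. If it is the date of last contact, the bias is zero.

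Nor should the settings in which all dropouts have a lag be read as expected values. Lost to follow-up is one of five withdrawal categories in Protocol 7.7.2. Voluntary and investigator withdrawals usually involve contact, and the protocol asks for Month 6 or early-termination procedures. Adverse events are collected until participation ends (Protocol 9), so some events in the lag may be learned of and counted, which would shrink the effect further.

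**Conclusion.** The two sections state different end dates for early leavers, and the direction of any bias under the literal 7.1.1 wording is certain: a lower rate and a lower upper bound. Its size is not established. It is zero if last contact is recorded as the discontinuation date, under 1% of the rate if a quarter of the dropouts have a lag of up to 60 days, and about 1.6% to 3% if all of them have 30 to 60 days. The corresponding one-sided error runs from 2.1–2.3% (no lag) through 2.5–2.8% and about 4% to 5–6%. These figures rest on the plan's 10% dropout, on assumed lags and shares, and on no event being learned of during the lag.

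This is a modest, conditional bias that would matter only for a result near 0.37 or 0.43. It is still worth correcting, because one stated rule for the primary denominator leans towards success and the planned analyses would not show it.

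Adopting 5.2 as it stands would not fully close the gap. A subject silent before day 180 but formally still in the study receives the full 180 days.

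**What to change.** Put one definition of exposure in SAP 5.2: it ends at the earliest of death, day 180 (or 365), and the last date on which HF hospitalisation and vital status were ascertained, taken from a visit, contact or event record. Apply it also to subjects with no contact up to day 180 who are formally still in the study. State that the study-completion form date is not used for subjects lost to follow-up.

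In 7.1.1, 7.1.6 and 7.1.11, replace the present wording with a reference to 5.2. SAP 7.1.4, 7.1.8, 7.1.9 and 7.1.12 then follow from 7.1.1. Optionally, add a sensitivity analysis of the primary endpoint that uses the recorded discontinuation date, so that the influence of the choice is visible.

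The cost is one derived date and a few lines of SAP text. The reported rate may be slightly less favourable than under the literal 7.1.1 wording.

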7.1.2. Sensitivity analysis

Sensitivity analyses using a negative binomial approach (with the same terms as the poisson model used in the main analysis) to capture within-subject correlation will be performed.

This document is confidential.

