7.1.3. Supplementary analysis

Then main analysis will be repeated based on the PP population and Cohort #1 population. Interpretation of the p-values will be done in descriptive manner only.

In addition, HFH and all-cause mortality from CEC adjudication results will be analysed separately using same method as the main analysis in Section [7.1.1](#). Secondary Efficacy Endpoints and Analyses

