7.1.4. Incidence of HF Hospitalizations or all-cause mortality at 12 months

The mathematical statement of the null and alternative hypothesis for the first secondary efficacy is as follows:

$$H_0: r_{12} \geq PG_{12}$$

$$H_A: r_{12} < PG_{12}$$

where r_{12} is the 12 month rate of secondary endpoint events and PG_{12} is the performance goal. A value of 0.70 will be used for the goal. The null hypothesis will be rejected if the upper confidence bound for the rate is less than the performance goal, or equivalently, that the corresponding p-value from the hypothesis test is less than 0.025. An observed value of less than 0.59 and rejection of the null will indicate that the observed rate is statistically less than the performance goal, indicating clinically acceptable results.

Analysis will be based on a Poisson regression approach for the number of events, with the log follow-up time as an offset term. Sensitivity analyses using a negative binomial approach to capture within-subject correlation will be performed.

12 month incidence of HF related hospitalizations (HFH) or all-cause mortality will be analyzed on the mITT, PP and Cohort #1 population in a similar manner to the primary efficacy endpoint.

7.1.5. Number of HF Hospitalizations at 6 and 12 months post-implant compared to the number of HF Hospitalizations in the 6 and 12 months prior to implant

Heart Failure hospitalizations will be summarized by cohort presenting number of subjects without any hospitalizations at 6 and 12 months post-implant visit, number of subjects with any hospitalizations at 6 and 12 months post-implant visit, number of hospitalizations per subject at 6 and 12 months post-implant visit, and mean number of hospitalizations per subjects at 6 and 12 months post-implant visit. Similar presentation will be done based on the CRF information on the number of hospitalizations in the 6 and 12 months prior to implant. 95 % Clopper-Pearson confidence interval (CI) will be provided in addition for the frequencies as applicable. In additional, Wilcoxon rank sum tests will be performed to compare the number of hospitalizations per subject at 12 months post-implant visit with 12 months prior-implant visit, and compare the number of hospitalizations per subject at 6 months post-implant visit with 6 months prior-implant visit.

The 6 and 12 months timepoint is independently of visit information and is calculated as:

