    model number of events = trt/ type3 dist= poisson offset=log(exposure_time);  
run;
```

Analysis will be done based on the Comparison population.

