7.1.7. Change of NT-proBNP from Baseline through 6 and 12 months

Change of NT-proBNP from baseline through 6 and 12 months will be presented by means of descriptive statistics at all study visits as described in [Appendix 1: Time and Event Schedule](#).

Analysis will be done based on mITT population, PP population, and Cohort #1 population. Prior to the date of cut-off for the main analysis, it will be confirmed, if analysis based on PP population will be required.

7.1.8. Combined outcome of: a. First and recurrent HF Hospitalizations b. HF Emergency Department/ Hospital Outpatient IV diuretic visits c. all-cause mortality at 6 months

Number of total events will be calculated as the sum of the number of HF hospitalizations, HF emergency department/hospital outpatient IV diuretic visits and all-cause mortality. Both first and recurrent events will contribute to the total number. All events will be equal weighting.

This endpoint will be analyzed similarly as the primary endpoint in Section [7.1.1](#).

Analysis will be done based on mITT population, PP population and Cohort #1 population. Prior to the date of cut-off for the main analysis, it will be confirmed, if analysis based on PP population will be required.

This document is confidential.

7.1.9. Heart failure hospitalization or HF Emergency Department / Hospital Outpatient IV diuretic visits at 6 and 12 months

Number of total events will be calculated out of number of HF hospitalizations or HF emergency department/hospital outpatient IV diuretic visits at 6 and 12 months. First and recurrent events will account to the total number. All events will be equal weighting.

This endpoint will be analyzed similarly as the primary endpoint in Section [7.1.1](#).

In addition, time to first HF hospitalization/ time to first HF emergency department/hospital outpatient IV diuretic visit in days will be defined as the time from date of Implant visit to the date of the event. In case of no event during the observation period, subject will be censored on the last available date.

Definition of time to first HF hospitalization (days):

In case of event, time to first HF hospitalization = [(Date of event – date of Implant visit) + 1]

In case of no event, time to HF hospitalization = [(Date of last available date – date of Implant visit) + 1], this data will be censored.

Definition of time to first HF emergency department/hospital outpatient IV diuretic visit (days):

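### The code for the primary test in SAP 7.1.1 leaves out the goal of 0.43, so its p-value is not equivalent to the upper confidence bound lying below 0.43

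*SAP*

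**What the plan says.** SAP 7.1.1 sets H0: r6 ≥ PG6 against HA: r6 < PG6, with a goal of 0.43. H0 is rejected if the upper confidence bound is below the goal, "or equivalently, that the corresponding p-value from the hypothesis test is less than 0.025". Success also requires an observed rate below 0.37. The estimate, its two-sided 95% CI and the p-value will all be presented.

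The test is said to use each subject's "total number of events, treatment arm, and exposure time", although the trial now has one arm. The code is a no-intercept Poisson model, "model number of events = dummy /*(dummy variable)*/ / noint type3 dist=poisson", with log exposure time as offset. SAP 5.2 defines exposure in days, capped at 180 or 365.

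Other sections refer back to this method:

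- 7.1.2 fits the negative binomial model "with the same terms as the poisson model used in the main analysis".
- 7.1.4 restates the hypotheses for 12 months with a goal of 0.70 and a limit of 0.59, gives no code, and says the endpoint "will be analyzed on the mITT, PP and Cohort #1 population in a similar manner to the primary efficacy endpoint".
- 7.1.3 says adjudicated HF hospitalizations and deaths "will be analysed separately using same method as the main analysis in Section" 7.1.1, and states no goal for either.
- 7.1.8, 7.1.9 and 7.1.12 each say: "This endpoint will be analyzed similarly as the primary endpoint in Section" 7.1.1. None states a goal.

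**The concern.** In a no-intercept model with one constant term and offset log(exposure), the default Wald and type 3 tests are of coefficient = 0. That is a rate of one event per unit of exposure. No non-zero constant coding of the dummy turns this into a test of 0.43; the goal has to enter through the offset or an ESTIMATE statement. The default p-value is also two-sided, while the plan tests one-sided at 0.025.

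What is at stake is the reporting. A number labelled as the primary hypothesis test would be close to zero whether the trial met its goal or missed it, and could contradict the bound printed beside it. The negative binomial model is there to show whether the result survives within-subject correlation. Its p-value, coded the same way, could not show that.

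**Working it through.** **Inputs.** Goal 0.43, limit 0.37, one-sided alpha 0.025, assumed rate 0.34, 450 implanted and 406 evaluable (Protocol 10.3; SAP 2.4.1 and 7.1.1). Exposure of 180 or 365 days (SAP 5.2). 12-month goal 0.70 and limit 0.59 (SAP 7.1.4). Full exposure is assumed below. The 428 case is an assumed midpoint, (406 + 450)/2, for partial follow-up of dropouts.

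**The plan's own figure.** With an exact one-sample Poisson test at n = 406, the largest count that rejects 0.43 is 148 (rate 148/406 = 0.3645, error 2.2%). Power at 0.34 is 81.4%, so the stated power above 80% is reproduced.

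**Formulas.** With E events in n subjects and r = E/n:

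- Coded test: z = ln(r/u) × √E, where u is the length of six months in the chosen exposure unit (180 for days, 6 for months, 1 for 6-month units).
- Test against the goal: z = ln(r/0.43) × √E.
- Upper bound: r × exp(1.96/√E).

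**At an observed rate of exactly 0.43.** n = 406 gives √(406 × 0.43) = 13.21, and n = 450 gives 13.91.

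- Days: ln(0.43/180) = -6.037, so z = -79.8 or -84.0.
- Months: z = -34.8 or -36.7.
- 6-month units: ln(0.43) = -0.844, so z = -11.2 or -11.7.

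**Coded test and bound side by side (n = 406, days).**

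| Events | Rate | Upper bound | Bound below 0.43? | Coded z | z against 0.43 | One-sided p against 0.43 |
|---|---|---|---|---|---|---|
| 138 | 0.340 | 0.402 | yes | -73.7 | -2.76 | 0.0029 |
| 148 | 0.365 | 0.428 | yes | -75.5 | -2.01 | 0.022 |
| 150 | 0.369 | 0.434 | no | -75.8 | -1.86 | 0.032 |
| 175 | 0.431 | 0.500 | no | -79.8 | 0.03 | 0.51 |
| 203 | 0.500 | 0.574 | no | -83.9 | 2.15 | 0.98 |

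Tested against the goal, the one-sided p is below 0.025 exactly when the bound is below 0.43. Sidedness matters too: at 148 events the bound passes, but the two-sided p against the goal is 2 × 0.022 = 0.044.

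**Across results.** Taking 60 to 399 events at n = 406, 428 and 450 gives 3 × 340 = 1,020 cases. The bound fails in 726. In days or months, the coded test rejects in all 726. In 6-month units it rejects in 681 of them (one-sided) or 669 (two-sided p < 0.025); there it still rejects up to an observed rate of 0.90 to 0.91 (one-sided) or about 0.89 (two-sided). With the goal in the offset there are no disagreements.

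**Negative binomial, same terms.** SE = √((1/0.43 + k)/n). The documents give no dispersion, so k = 0.25 to 2 is assumed. At an observed 0.43, z runs from -58 to -80 in days, or from -8.2 to -11.2 in 6-month units.

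**12 months, observed rate exactly 0.70.** ln(0.70/365) × √(n × 0.70) gives z = -105.5 (406) or -111.0 (450) in days. In 12-month units it is -6.0 or -6.3.

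**Effect on success if the coded p-value replaced the bound.** Only the 0.37 limit would then bind.

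| n | Largest count passing bound and 0.37 | Largest count passing 0.37 alone | Error at a true rate of 0.43 |
|---|---|---|---|
| 406 | 148 | 150 | 2.2% and 3.2% |
| 428 | 157 | 158 | 2.3% and 2.8% |
| 450 | 166 | 166 | 2.4% in both |

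These errors assume Poisson counts. At 12 months the bound allows 251 (406) or 280 (450) events, and the 0.59 limit allows 239 or 265. The limit binds first, so nothing changes.

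**The case against.** The code is plainly schematic: the data set name and the dummy are placeholders. The prose states the hypothesis, the goal, the bound rule and the 0.37 limit, and it describes the p-value as coming from that hypothesis test. On this reading the snippet is merely incomplete, and a competent programmer would add the goal. If the exposure variable were pre-scaled by 0.43/180, the test would be right.

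Much of this stands. The prose is correct and the bound can be computed from the coded model. But the snippet is the only specification of how the p-value is obtained, SAP 5.2 defines exposure in days with no scaling by the goal, and raw SAS output is itself planned. The SAP index lists 25 such tables for the 6- and 12-month endpoints (13 and 12), so the default p-value would be seen.

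For endpoints without a goal, the plan already calls other secondary p-values nominal (Protocol 10.4, SAP 2.4.2) and the PP and Cohort #1 ones descriptive (SAP 7.1.3). Being analysed similarly does not strictly require a p-value. That lowers the stakes, but a nominal p-value still needs a stated null.

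A reader might also infer that 7.1.1 reuses the two-group code of 7.1.6 with the comparator removed. The documents do not show this: 7.1.6 has "model number of events = trt/ type3 dist= poisson offset=log(exposure_time") with a CLASS statement and an intercept, and there the default test does compare two groups.

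**Conclusion.** The point holds for the reported p-value. As coded, it does not test 0.43, is two-sided, and is not equivalent to the bound. In days or months it rejects whenever the bound fails. In 6-month units the disagreement is large but not complete (681 or 669 of 726).

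Two stronger conclusions are tempting and not supported. One is that the trial could be declared a success at almost any event rate. The bound and the 0.37 limit prevent that: even if the p-value replaced the bound, the threshold moves by at most two events and the error rises to 3.2% at n = 406. The other is that the negative binomial check is worthless. Its rate and interval can still be compared with 0.43; only its p-value is uninformative.

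The extension to 12 months is by reference and not by code, since 7.1.4 states its own goal. All this assumes that exposure is not pre-scaled by the goal and that the software's default test is reported. It should be corrected before the main analysis is reported, but it does not threaten the design.

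**What to change.** - In 7.1.1, fit an intercept-only Poisson model with offset log(0.43 × exposure/180), or use an equivalent ESTIMATE against the goal. At 12 months use log(0.70 × exposure/365).
- Report the one-sided p-value for intercept = 0. Report the bound as the goal × exp(upper limit of the two-sided 95% CI for the intercept). The two then agree by construction.
- Use the same offset in the negative binomial model of 7.1.2.
- Delete the reference to treatment arm in 7.1.1.
- Where there is no goal (the separate components in 7.1.3, and 7.1.8, 7.1.9 and 7.1.12), report the rate and CI without a p-value.

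The cost is a few lines of SAS and two or three sentences of SAP text. The estimate, the bound, the success rule and the sample size do not change, and exact power at 0.34 with 406 subjects stays at 81.4%.
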